## **2 STUDY OBJECTIVES**

### **2.1 Primary Objective**

The primary objective is the evaluation of  $\alpha_v\beta_6$  receptor occupancy by PLN-74809 in the lungs, as assessed by changes from baseline in  $\alpha_v\beta_6$  PET tracer uptake patterns following a single dose.

Analyses of the PET imaging data will be detailed in a separate statistical analysis plan (SAP), written by [REDACTED].

### **2.2 Secondary Objectives**

The secondary objective is the assessment of the safety and tolerability of PLN-74809 in IPF participants.

### **2.3 Exploratory Objectives**

[REDACTED]  
[REDACTED]

|  |  |  |
|--|--|--|
|  |  |  |
| Confidentiality Statement   |  |  |
| This document is the property of [REDACTED] and may not be duplicated, copied, altered or removed from company without prior approval from [REDACTED] or in compliance with [REDACTED] |  |  |

This document is the property of [REDACTED] and may not be duplicated, copied, altered or removed from company without prior approval from [REDACTED] or in compliance with [REDACTED]

[REDACTED]

|  |  |                  |                         |
|--|--|------------------|-------------------------|
|  |  | Sponsor:         | Pliant Therapeutics Inc |
|  |  | Protocol Number: | PLN-74809-IPF-201       |
| STATISTICAL ANALYSIS PLAN – PHASE 1 |  |                  |                         |

### **3 ENDPOINTS**

#### **3.1 Primary Endpoint**

The primary endpoint is the changes from baseline in  $\alpha v\beta 6$  PET tracer uptake patterns following a single dose.

Analyses of the PET imaging data will be detailed in a separate analysis plan, written by [REDACTED]

#### **3.2 Secondary Endpoints**

1. Incidents of Treatment-Emergent Adverse Events (TEAE)
2. Change from baseline in clinical safety laboratory measures
3. Change from baseline in vital signs
4. [REDACTED]

#### **3.3 Exploratory Endpoints**

[REDACTED]  
[REDACTED]

|  |  |  |
|--|--|--|
|  |  |  |
| Confidentiality Statement   |  |  |
| This document is the property of [REDACTED] and may not be duplicated, copied, altered or removed from company without prior approval from [REDACTED] or in compliance with [REDACTED] |  |  |

|  |  |                  |                         |
|--|--|------------------|-------------------------|
|  |  | Sponsor:         | Pliant Therapeutics Inc |
|  |  | Protocol Number: | PLN-74809-IPF-201       |
| STATISTICAL ANALYSIS PLAN – PHASE 1 |  |                  |                         |

## 4 SAMPLE SIZE

The sample size has been set empirically. Up to 12 participants should provide proof of concept on the ability of the study to assess target engagement ( $\alpha_v\beta_6$  receptor occupancy by PLN-74809). Pharmacodynamic (PD), pharmacokinetic (PK), and safety/ tolerability evaluation of PLN-74809 will be assessed in the target population.

|  |  |
|--|--|
| Confidentiality Statement   |  |
| This document is the property of [REDACTED] and may not be duplicated, copied, altered or removed from company without prior approval from [REDACTED] or in compliance with [REDACTED] |  |

|  |  |                  |                         |
|--|--|------------------|-------------------------|
|  |  | Sponsor:         | Pliant Therapeutics Inc |
|  |  | Protocol Number: | PLN-74809-IPF-201       |
| STATISTICAL ANALYSIS PLAN – PHASE 1 |  |                  |                         |

## 5 RANDOMIZATION

Not applicable. This a non-randomized, open-label study.

|  |            |
|--|------------|
| Confidentiality Statement   |            |
| This document is the property of [REDACTED] and may not be duplicated, copied, altered or removed from company without prior approval from [REDACTED] or in compliance with [REDACTED] | [REDACTED] |

|  |  |                  |                         |
|--|--|------------------|-------------------------|
|  |  | Sponsor:         | Pliant Therapeutics Inc |
|  |  | Protocol Number: | PLN-74809-IPF-201       |
| STATISTICAL ANALYSIS PLAN – PHASE 1 |  |                  |                         |

## 6 PLANNED ANALYSES

### 6.1 Analysis Populations

Participants excluded from the analysis populations and the reason for their exclusion will be listed in Appendix 16.2 of the clinical study report (CSR).

#### 6.1.1 Screened Participants

Screened Participants are any participants who gave informed consent to participate in the study.

#### 6.1.2 Intention to Treat (ITT) Population

All participants enrolled in the study (passed screening) will be included in the ITT Population.

#### 6.1.3 Safety Population

All participants who receive at least 1 dose of study drug will be included in the Safety Population.

#### 6.1.4 Modified Intention to Treat (mITT) Population

All dosed participants with at least baseline and at least 1 post-baseline PET scan will be included in the mITT population.

The mITT Population will not be used for any analyses listed in this SAP, with the exception of participant disposition.

#### 6.1.5 PK Concentration Population

All participants who receive at least 1 dose of study drug and have any measurable PLN-74809 concentration data will be included in PK Concentration Population.

#### 6.1.6 PK Analysis Population

All participants who have sufficient PLN-74809 concentration data for PK calculation will be included in the PK Analysis Population.

### 6.2 Derived Data

This section describes the derivations required for statistical analysis. Unless otherwise stated, variables derived in the source data will not be re-calculated.

|  |  |                                  |  |
|--|--|----------------------------------|--|
|  |  | Confidentiality Statement |  |
| This document is the property of [REDACTED] and may not be duplicated, copied, altered or removed from company without prior approval from [REDACTED] or in compliance with [REDACTED] |  |                                  |  |

|  |  |                  |                         |
|--|--|------------------|-------------------------|
|  |  | Sponsor:         | Pliant Therapeutics Inc |
|  |  | Protocol Number: | PLN-74809-IPF-201       |
| STATISTICAL ANALYSIS PLAN – PHASE 1 |  |                  |                         |

### **6.2.1 Race**

Where more than 1 race category has been selected for a participant, these race categories will be combined into a single category labeled “Multiple Race” in the summary tables. The listings will reflect the original selected categories.

### **6.2.2 Body Mass Index**

Body mass index (BMI) will be calculated as follows:

$$\text{BMI (kg/m}^2\text{)} = \text{Weight at screening (kg)} / [\text{Height at screening (m)}]^2$$

### **6.2.3 Baseline**

Baseline is defined as the last non-missing value (either scheduled, unscheduled or repeat) before the participant receives the first dose of study drug.

### **6.2.4 Dose-specific Baseline**

Dose-specific baseline is defined as the last non-missing value (either scheduled, unscheduled or repeat) before the participant receives the specific dose of study drug being analyzed.

### **6.2.5 End of Dosing Period**

For doses that are not a participant’s final dose of the study, end of dosing period is defined as the last non-missing visit prior the next dose.

For participants’ final dose of the study, end of dosing period is defined as the end of treatment (EOT)/ end of study (EOS) visit.

### **6.2.6 Gender, Age and Physiology (GAP) Index and Staging System**

The GAP index and staging system is a multidimensional prognostic staging system derived from 4 commonly measured clinical and physiologic variables (Gender, Age and 2 lung physiology variables (forced vital capacity [FVC] and diffusing capacity of the lungs for carbon monoxide [DLCO]). Points are allocated to each clinical or physiological variable and points are summed to provide a total score (from 0-8). The total score is then used to assign a stage (I, II, or III) as follows:

#### **GAP Scoring**

|                                  |  |  |  |
|----------------------------------|--|--|--|
|                                  |  | Confidentiality Statement   |  |
| This document is the property of |  | and may not be duplicated, copied, altered or removed from company without |  |
| prior approval from              |  |  |  |
| or in compliance with            |  |  |  |

|  |  |                  |                         |
|--|--|------------------|-------------------------|
|  |  | Sponsor:         | Pliant Therapeutics Inc |
|  |  | Protocol Number: | PLN-74809-IPF-201       |
| STATISTICAL ANALYSIS PLAN – PHASE 1 |  |                  |                         |

| Predictor               | Points Allocated   |
|--------------------------------|---|
| Gender                         | Female = 0
Male = 1  |
| Age                            | $\leq 60 = 0$
$61 - 65 = 1$
$> 65 = 2$                                    |
| Physiology – FVC, % Predicted  | $> 75 = 0$
$50 - 75 = 1$
$< 50 = 2$                                       |
| Physiology – DLCO, % Predicted | $> 55 = 0$
$36 - 55 = 1$
$\leq 35 = 2$
Cannot perform a = 3 |
| Total Point Score       | 0 - 8  |

a 'Cannot perform' is only assigned if symptoms or lung function prohibited performance of the DLCO maneuver. If DLCO is unavailable for a non-respiratory reason (eg, an operational reason), the GAP index and staging system cannot be applied.

#### Staging System

| Stage  | I | II | III |
|---------------|----------|-----------|------------|
| Points | 0 - 3    | 4 - 5     | 6 - 8      |

#### 6.2.7 Duration of Nintedanib and Pirfenidone

Duration of nintedanib will be calculated in months as: date of first dose of study drug – date of first dose of nintedanib.

Duration of pirfenidone will be calculated in months as: date of first dose of study drug – date of first dose of pirfenidone.

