4 STUDY POPULATION

4.1 Inclusion Criteria

Each participant must meet the following criteria to be enrolled in this study:

- 1. Participants aged 40 or older.
- 2. Confident diagnosis of IPF, within 8 years prior to Screening, according to the Fleischner Guidelines criteria; specifically either HRCT imaging showing a pattern of typical or probable usual interstitial pneumonia (UIP) or a histopathology specimen demonstrating a UIP pattern in the correct clinical context (and confirmed by multidisciplinary conference review at study site.
- 3. FVC percent of predicted ≥ 45%; historical FVC for entry in the study is permitted if within 1 month of screening.
- 4. Diffusing capacity for carbon monoxide (DLco) (hemoglobin-adjusted) ≥30%; historical DLco for entry in the study is permitted if within 1 month of screening.
- 5. Participants currently receiving treatment for IPF with nintedanib or pirfenidone are allowed, provided these drugs have been given at a stable dose for at least 3 months before the Screening Visit and are expected to remain unchanged during the study.
- 6. Female participants of nonchildbearing potential must be either surgically sterile (hysterectomy, bilateral tubal ligation, salpingectomy, and/or bilateral oophorectomy at least 26 weeks before the Screening Visit) or postmenopausal, defined as spontaneous amenorrhea for at least 2 years.
- 7. Female participants must have a negative pregnancy test at Baseline.
- 8. Female participants of childbearing potential (i.e., ovulating or premenopausal and not surgically sterile) and all male participants with sexual partners of childbearing potential must agree to use highly effective methods of birth control during their participation in the study and for 30 and 90 days, respectively, after the last administration of study drug. Hormonal contraceptives are not allowed. Highly effective methods of birth control are defined as those with 99% or greater efficacy
- 9. Participants must agree to abstain from sperm or egg donation through 90 or 30 days, respectively, after administration of the last dose of study drug.
- 10. Able to understand the purpose of the study and its procedures and to sign a written informed consent form.

[figure not shown]
Confidential Page 298 of 331

Pliant Therapeutics Inc.
Page 24

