5.8 Restrictions

5.8.1 Prior Therapy

Previous use of IPF standard-of-care treatment (pirfenidone or nintedanib) is allowed for participation in this study. Prohibited medications (see Section 5.7, Concomitant Therapy) should be stopped at least 5 half-lives before dosing on Day 1.

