### 6.6 Baseline Comparability

The comparability of doses with respect to participant demographics and baseline characteristics will be assessed in a descriptive manner, but no formal statistical testing will be performed.

Standard continuous or categorical variable summaries will be presented overall for the following variables based on the Safety Population:

- Age at Informed Consent (years),
- Sex (Male, Female),
- Fertility Status (Childbearing Potential, Post-menopausal, Surgically Sterile)
- Ethnicity (Hispanic or Latino, Not Hispanic or Latino),

|   |  |                                  |  |
|---|--|----------------------------------|--|
|   |  | Confidentiality Statement |  |
| This document is the property of [REDACTED] and may not be duplicated, copied, altered or removed from company without prior approval from [REDACTED] or in compliance with [REDACTED]. |  |                                  |  |

|  |  |                  |                         |
|--|--|------------------|-------------------------|
|  |  | Sponsor:         | Pliant Therapeutics Inc |
|  |  | Protocol Number: | PLN-74809-IPF-201       |
| STATISTICAL ANALYSIS PLAN – PHASE 1 |  |                  |                         |

- Race (American Indian or Alaska Native, Asian, Black or African American, Native Hawaiian or Other Pacific Islander, White, Multiple Race),
- Height at Screening (cm),
- Weight at Screening (kg),
- BMI at Screening (kg/m^2)
- Pulmonary Function at Screening,
- DLCO,
- GAP Staging,
- Months since IPF diagnosis,
- Received nintedanib as standard of care prior to randomization (Yes, No),
  - If yes, duration of nintedanib use (months),
- Received pirfenidone as standard of care prior to randomization (Yes, No),
  - If yes, duration of pirfenidone use (months)

All demographic and baseline characteristic data will be listed.

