## 6.8 Prior and Concomitant Medications and Non-Pharmacological Procedures

The number of prior and concomitant medications will be summarized by Anatomical Therapeutic Chemical (ATC) Classification level 4 term and preferred term for the Safety Population. Prior and concomitant medications will be summarized separately. Prior and concomitant medications and non-pharmacological procedures will be listed for the Safety Population. Medications will be coded using the World Health Organization Drug Dictionary (WHODD) [REDACTED] ATC Classification System level 4 term and preferred term.

Prior medications are defined as all medications starting and stopping before the date of first dose of study drug. Concomitant medications are defined as medications taken on or after the date of first dose of study drug.

|  |  |                                  |  |
|--|--|----------------------------------|--|
|  |  | Confidentiality Statement |  |
| This document is the property of [REDACTED] and may not be duplicated, copied, altered or removed from company without prior approval from [REDACTED] or in compliance with [REDACTED] |  |                                  |  |

|  |  |                  |                         |
|--|--|------------------|-------------------------|
|  |  | Sponsor:         | Pliant Therapeutics Inc |
|  |  | Protocol Number: | PLN-74809-IPF-201       |
| STATISTICAL ANALYSIS PLAN – PHASE 1 |  |                  |                         |

Use and duration of Pirfenidone and Nintedanib will be summarized overall using standard continuous or categorical variable summaries.

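### SAP 6.2.7 measures time since first nintedanib or pirfenidone dose but reports it as duration of use, which overstates duration for former users and switchers

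*SAP*

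**What the plan says.** SAP 6.2.7 gives one formula per drug. For nintedanib: "Duration of nintedanib will be calculated in months as: date of first dose of study drug – date of first dose of nintedanib". For pirfenidone: "Duration of pirfenidone will be calculated in months as: date of first dose of study drug – date of first dose of pirfenidone". Neither includes a stop date, an interruption rule or a condition that the participant is still taking the drug.

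The variable is reported in two places. SAP 6.6 lists a Yes/No baseline item for each drug, "Received nintedanib as standard of care prior to randomization (Yes, No") and "Received pirfenidone as standard of care prior to randomization (Yes, No"), each followed by duration of use in months for those answering Yes. SAP 6.8, which covers prior and concomitant medications, adds: "Use and duration of Pirfenidone and Nintedanib will be summarized overall using standard continuous or categorical variable summaries".

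On who may enrol, Protocol 5.8.1 says: "Previous use of IPF standard-of-care treatment (pirfenidone or nintedanib) is allowed for participation in this study". Inclusion criterion 5 in Protocol 4.1 says "Participants currently receiving treatment for IPF with nintedanib or pirfenidone are allowed". It then attaches a stability condition to that current treatment only: "provided these drugs have been given at a stable dose for at least 3 months before the Screening Visit".

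**The concern.** Subtracting the first antifibrotic dose date from the first study-drug dose date gives the time elapsed since the drug was started. It is the time on the drug only if the participant never stopped. Someone who tried pirfenidone for a few months years ago is credited with every month since. Someone who moved from one antifibrotic to the other answers Yes twice and receives two durations covering the same calendar months.

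At stake is the accuracy of the description of background therapy. Nintedanib and pirfenidone are the standard-of-care treatments that the protocol names and allows. With at most 12 participants, one misreported duration can visibly move a mean. A smaller, editorial matter is that both items in 6.6 refer to randomization, while SAP section 5 says the study is non-randomized.

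**Working it through.** The plan gives no figure to reproduce. The sample size is empirical and no hypothesis is tested, so the check is date arithmetic.

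**Inputs from the documents**
- Duration formulas: SAP 6.2.7.
- Duration is reported for everyone who received the drug: SAP 6.6, and again in 6.8.
- Former use is allowed: Protocol 5.8.1.
- A current antifibrotic must have been at a stable dose for at least 3 months before Screening: Protocol 4.1, criterion 5.
- Screening is up to 35 days before dosing and may share a day with the Day -7 Baseline visit: Protocol 3.4.
- Diagnosis is at most 8 years before Screening: Protocol 4.1, criterion 2.
- Up to 12 participants: SAP section 4.

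**Assumed:** 30.4375 days per month (6.2.7 gives no divisor), and the treatment histories in the examples.

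**Formulas.** Let D be the first study-drug dose date, A the antifibrotic start date and S its stop date.
- SAP duration = D − A
- Time on drug, for a single course = min(S, D) − A
- Overstatement = D − S if S is before D, otherwise 0

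**Bounds on the overstatement**
- *Uninterrupted current user:* 0.
- *Direct switcher* (the earlier drug stops when the current one starts): the current drug has been taken for at least 3 months before Screening. The earlier drug is therefore overstated by at least 3 + 7/30.4375 = 3.2 months if Screening is 7 days before dosing, or 3 + 35/30.4375 = 4.2 months (4.15 before rounding) if it is 35 days before.
- *Former user now on neither drug:* from near 0 up to about 96 + 35/30.4375 = 97 months. The upper end assumes treatment began no earlier than diagnosis and was stopped almost at once.

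**Examples (assumed histories, in months)**

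| History before first study dose | SAP | Time on drug | Ratio |
|---|---|---|---|
| 12 on drug, still taking it | 12 | 12 | 1.00 |
| 12 on drug, stopped 4 before | 12 + 4 = 16 | 12 | 1.33 |
| 12 on drug, stopped 24 before | 12 + 24 = 36 | 12 | 3.00 |

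A participant on pirfenidone from month -36 to month -24, then on nintedanib up to dosing, gets 36 + 24 = 60 drug-months from the SAP. The time actually treated is 12 + 24 = 36.

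**Effect on the mean.** One affected user among n users of that drug shifts the mean by (D − S)/n.

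| Gap D − S | n = 3 | n = 6 | n = 12 |
|---|---|---|---|
| 4 months | 1.33 | 0.67 | 0.33 |
| 24 months | 8.0 | 4.0 | 2.0 |

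**The case against.** The strongest reply is that little depends on this variable, and most of that reply stands.

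- A reader might infer that no output shows which antifibrotic a participant was taking around dosing. The documents do not support that. SAP 6.8 summarizes prior and concomitant medications separately by preferred term, with prior meaning started and stopped before the first study dose, and it lists both. Current and stopped use may therefore be visible there already.
- A reader might infer that the number on treatment is overstated. The 6.6 item is labelled as receipt beforehand, which is ever-use. An ever-use count is not a wrong count of current use.
- A reader might infer that comparisons of receptor occupancy or PK by background therapy are compromised. The SAP plans no PK or safety analysis using this variable, and PET analysis sits in a separate plan that is not among the documents.
- The number affected is unknown and could be zero. The SAP also reports median, minimum and maximum, so an extreme value would not be hidden behind the mean.
- Protocol 5.7 records medications taken in the 30 days before Screening. A drug stopped earlier may not be captured unless the eCRF collects antifibrotic history separately, and the eCRF is not among the documents. If it is not captured, the former user gets no duration at all.

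None of this repairs the formula. For any former user or switcher whose start date is recorded, 6.2.7 gives a wrong number under the label of duration. The last point bears on the fix: it decides whether a stop date can be used or the variable has to be narrowed.

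**Conclusion.** The point holds, and it is minor. The rule in SAP 6.2.7 is wrong for part of the population the protocol admits, and right for uninterrupted current users. For each former user or switcher the error is exactly the gap between stopping the antifibrotic and the first study dose: at least 3.2 to 4.2 months for the earlier drug of a direct switcher, and anywhere from near 0 to about 97 months for someone now on neither drug. These bounds rest on the timing assumptions stated with them. The mean shifts are illustrations, because neither the number of affected participants nor their histories are given.

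The effect is confined to descriptive summaries of baseline characteristics and medication. It reaches no primary, PK or safety result planned in this SAP. Confidence is high that the formula lacks a stop date, and low about how many values would change.

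**What to change.** - In SAP 6.2.7, define duration as min(antifibrotic stop date, first study-drug dose date) minus antifibrotic start date, summing separate courses where more than one is recorded. Use the same derivation in 6.6 and 6.8. Values for uninterrupted current users do not change.
- If stop dates for past use are not collected, either restrict the variable to participants on the drug at the first study dose, or relabel it *time since first use*.
- Leave duration missing for a former user whose stop date is wholly unknown. The stop-date imputation in 6.2.10.1 falls back on the last clinic visit in the study; under the new formula, that would bring back the overstated value.
- In 6.6, replace each Yes/No item with three levels: receiving at first study dose, previous use only, never.
- In 6.6, refer to the first dose of study drug in place of randomization. This is editorial.

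The cost is a few lines of SAP text and one derivation, provided stop dates are in the database. The eCRF should be checked first, given the 30-day look-back. If the dates are absent, restricting or relabelling the duration needs no new data, but the previous-only level is complete only if past use was recorded.
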